11. ADMINISTRATIVE MATTERS

11.1 Source Data

Source documents comprise the CRF and hospital records, laboratory records and correspondence. All documents will be stored safely in a confidential manner at the performing site. The subject will be referred to by a unique study subject number/code, their initials and date of birth on all study-specific documentations. The only exceptions will be the signed Consent Forms, Subject Identification log and subject clinical file, all of which will be stored securely by the clinical site. Source data will be made available for internal and external audits or inspections by regulatory authorities to authorised personnel only. As a minimum requirement the following data must be source data verifiable in source documentation other than the eCRF:

- Existence of subject (subject identifier, subject number and date of birth)
- Confirmation of participation in the trial (subject identification number (ID), trial ID and signed and dated informed consent forms)
- Diagnosis/ indication under investigation
- Visit dates
- Data from AEs, safety information form and pregnancy forms
- Relevant medical history, concomitant illness
- Reason for exclusion or withdrawal

11.2 Language

CRFs will be in German. Generic names for concomitant medications should be recorded in the CRF wherever possible. All written material to be used by subjects must use vocabulary that is clearly understood, and be in the language appropriate for the study site.

11.3 Data Collection

All data collected will be documented in the source documents and eCRF (HybridForms®).

11.4 Electronic Recording of data

This study will capture and process data using HybridForms® (electronic data capture) which will be built by Kapsch Business Com AG, Graz, Austria. HybridForms® is a fully validated high quality electronic data capture system, which has a full audit trail and controlled level of access. Data and reports will be extracted from the database throughout the study to monitor progress and training will be provided to all study staff on use of the database. The Investigator must ensure that the data is recorded in the eCRFs as soon as possible after the visit preferably within 7 working days.

11.5 Study Management Structure

11.5.1 Trial Steering Committee (TSC)

A Trial Steering committee (TSC) comprised by all principal investigators and chaired by the Chief investigator will be responsible for overseeing the progress of the trial. A TSC Charter will be devised to list the roles and responsibilities of the TSC members. TSC will be convened at least biannually either in person or by teleconference.

11.6 Monitoring

A monitoring plan will be devised based on risk analysis and described in detail in the monitoring manual. During the course of the trial the Monitor will visit the trial sites to ensure that the protocol is adhered to, that all issues have been recorded and to perform source data verification. The study will be monitored periodically by a Clinical Trial Monitor responsible for this study.

Initiation visits will be completed at all trial centres prior to the recruitment of participants, and will consist of review of protocol and trial documents, training with respect to trial procedures (informed consent, SAE reporting, inclusion and exclusion criteria), review of recruitment strategy, review of site facilities and equipment, review of GCP principles, essential document receipt, collection and filing, and archiving and inspection. Copies of the trial specific procedure manuals and related documents will be given to the investigators. The approved version of the protocol should be followed at all times, and any significant protocol deviations will be documented in a Protocol Deviation Form and any significant deviations will be recorded on a Protocol Violation Form submitted to the study coordination centre and Sponsor as soon as possible. The investigators will allow the monitors to:

- inspect the site, the facilities, device management and materials used for the trial
- meet all members of the team involved in the trial, and ensure all staff working on the trial are experienced and appropriately trained, and have access to review all of the documents relevant to the trial
- have access to the electronic case record forms and source data

- discuss with the investigator and site staff trial progress and any issues on a regular basis

The monitor will ensure that:

- A percentage of records will be inspected for confirmation of existence, eligibility based on the results of the Risk Assessment
- 100 % of consent forms will be reviewed along with all SAE's.
- there is adherence to the protocol, including consistency with inclusion/exclusion criteria
- there is GCP and regulatory compliance
- trial documentation is complete and up to date (e.g. correct versions of documents being used, source data captured) and relevant documents are collected for the Trial Master File (TMF)
- the monitored eCRFs have been completed correctly and accurately, and all entries correspond to data captured in source documents

The Monitor must be given direct access to the source documents (original documents, data and records). Direct access includes permission to examine, analyse, verify and reproduce and record reports that are important to evaluation of the clinical trial.

All information dealt with during such visits will be treated as strictly confidential. At the end of the trial, close out visits will be performed by the monitor after the final participant visit has been completed and prior to database lock. During this visit the monitor will verify that all trial close out activities are completed – all queries resolved, missing data completed, monitoring completed, archiving arrangements in place, ISF completed and TMF documents collected, and end of trial notification. Each investigator will also be notified that an audit or inspection may be carried out - by the sponsor, sponsor's representatives or the host institution, or regulatory authorities - at any time, before, during or after the end of the trial. The investigator must allow the representatives of the audit or inspection team:

- to inspect the site, facilities and material used for the trial,
- to meet all members of his/her team involved in the trial,
- to have direct access to trial data and source documents, to consult all of the documents relevant to the trial. If an Investigator is informed of an impending audit or inspection, the trial coordination centre should be notified immediately.

11.7 Disclosure of data and publication

Information concerning the study, patent applications, processes, scientific data or other pertinent information is confidential and remains the property of the Sponsor. The investigator may use this information for the purposes of the study only. Verbal or written discussion of results prior to study completion and full reporting should only be undertaken with written consent from the Sponsor. Therefore all information obtained as a result of the study will be regarded as CONFIDENTIAL, at least until appropriate analysis and review by the investigators is completed. Permission from the Trial Steering Committee is necessary prior to disclosing any information relative to this study outside of the Steering Committee.

**Ertugliflozin to Reduce Arrhythmic burden in ICD/CRT patients (ERASE-Trial) – a phase III Study**

**Abbreviations and Definitions**

6MWT	6-minute walk test
AESI	Adverse events of Special Interest
ALAT	Alanine-Aminotransferase
ASAT	Aspartate-Aminotransferase
BASG	Bundesamt für Sicherheit im Gesundheitswesen
BMI	Body mass index
CHF	Congestive Heart Failure
CLTR	Department for Clinical Trials
CRF	Case Report Form
CRT	Cardiac resynchronisation therapy
CV	Cardiovascular
DCM	Dilative cardiomyopathy
DKA	Diabetic Ketoacidosis
ECG	Electrocardiogram
eCRF	Electronic Case Report Form
eGFR	Estimated Glomerular Filtration Rate
EMA	European Medicine Agency
EudraCT	European Union Drug Regulating Authorities Clinical Trials
FDA	Food and Drug Administration
FPFV	First Patient First Visit
GCP	Good Clinical Practice
GGT	Gamma-Glutamyl-Transferase
HDL	High Density Lipoprotein
ICD	Internal cardioverter defibrillator
IMI	Institute of Medical Informatics, Statistics and Documentation
ISF	Investigator Site File

**Ertugliflozin to Reduce Arrhythmic burden in ICD/CRT patientS (ERASE-Trial) – a phase III Study**

INS	Institute Surveillance
KKS	Koordinierungszentrum für Klinische Studien
LBBB	Left bundle branch block
LDL	Low Density Lipoprotein
LPLV	Last Patient Last Visit
MCI	Myocardial infarction
nsVT	Non sustained ventricular tachycardia
nt-proBNP	N-terminal pro b-type natriuretic peptide
NYHA	New York Heart Association
pH	Podus Hydrogenii
QoL	Quality of life
RR	Riva Rocci Blood Pressure Measurement
SGLT-2	Sodium-dependent glucose cotransporter 2
SUSAR	Suspected Unexpected Serious Adverse Reaction
SVT	Sustained ventricular tachycardia
T2DM	Type 2 Diabetes Mellitus
TMF	Trial Master File
TMG	Trial Management Group
TSC	Trial Steering Committee
ULN	Upper Limit of Normal
UTI	Urinary Tract Infection
VF	Ventricular fibrillation
VT	Ventricular tachycardia
ULN	Upper Limit of Normal
UTI	Urinary Tract Infection

## **Ertugliflozin to Reduce Arrhythmic burden in ICD/CRT patientS (ERASE-Trial) – a phase III Study**

### **1 Introduction and rationale**

**Sodium-dependent glucose cotransporter 2 (SGLT2) is mainly expressed in human kidneys and small intestinal cells. In the proximal tubule of the nephron SGLT2 is responsible for the reabsorption of approximately 90% of the filtrated glucose. Inhibition of SGLT2 was shown to increase renal glucose excretion and to lower glucose. Subsequently, a number of SGLT-2 inhibitors were developed and are currently approved for the treatment of type 2 diabetes. CV outcome trials, required by the European Medicines Agency (EMA) and Federal Drug Administration (FDA) have proven additional beneficial effects on cardiovascular outcome in various compounds of that class. Empagliflozin could even show significant positive effects on mortality(1). More consistent and most pronounced was the effect of reducing heart failure hospitalisation. Most recently, data of dapagliflozin was published (DAPA-HF)(2) extending these beneficial effects to non-diabetic heart failure patients, significantly reducing the primary endpoint of CV death and worsening heart failure as well as CV-mortality alone and even all course mortality. As dose-response modelling indicates that ertugliflozin 5 mg and 15 mg result in near maximal urinary glucose excretion (UGE) in patients with type 2 diabetes mellitus, providing 87% and 96% of maximal inhibition, respectively (product information Steglatro), the lower dose can be expected to be comparably efficient and will therefore be used in this study. This is also confirmed by the data of a recent pooled analysis of previous phase III trials with ertugliflozin showing a reduction in HbA1c of only 0.1% (3). Ventricular arrhythmias are a typical feature of advanced heart failure with reduced ejection fraction (HFrEF) or heart failure with mid-range ejection fraction (HFmrEF), and account for a large proportion of cardiac death in this population. Implantation of an ICD is a class IA recommendation in the ESC heart failure guidelines both in secondary prevention and primary prevention (IB for DCM patients)(4). Additional CRT function is a class IA recommendation in all of these patients with QRS duration >150ms in sinus rhythm(4). Since arrhythmias occur independent of the type of cardiomyopathy (ischemic, dilative, idiopathic) the unifying phenotype of altered contractility and elevated diastolic pressure and potentially increased systemic inflammation itself must be regarded as the trigger of these arrhythmias(5). Therefore,**

**Ertugliflozin to Reduce Arrhythmic burden in ICD/CRT patientS (ERASe-Trial) – a phase III Study**

every improvement of heart failure should result in a reduction of ventricular arrhythmias. This has been shown extensively for beta-blockers(6), aldosterone-antagonists(7; 8), and ARNIs(9; 10). Large outcome studies with ACE Inhibitors did only give limited insight in the type of arrhythmic events, their causes, and the effect of the treatments(11; 12), while studies analysing the rate of ventricular arrhythmias did show a significant reduction in these events(13). Previous data showed that SGLT-2 inhibitor dapagliflozin (DAPA-HF) improved primary outcome in a HFrEF population comparable to sacubitril/valsartan in the PARADIGM trial(9) (both trials with a NNT of 21). Therefore, a comparable impact on heart failure morbidity and ventricular arrhythmias can be assumed for both drugs. Moreover, Martens et al. reported on a highly significant reduction of ventricular arrhythmias after initiation of sacubitril/valsartan in a retrospective analysis of 151 patients with an observation period of 6 months. The number of VT/VF episodes declined by more than two thirds (10).

Mortality in patients on ICD therapy is high despite optimal medical treatment. The study by Martens is a retrospective analysis of data of patients that were followed throughout the observation period of 364 days.

Therefore, severely ill patients and at least those who died within these 12 months were not analysed. Obviously, these patients tend to have the highest burden of ventricular arrhythmias. Therefore, event rate in the Martens study is underestimated.

More reliable data on event rates derive from prospective randomized trials such as the RAFT study. They report a rate of VTs of ~2 per year (11278 appropriate ICD detections in 5953.6 patient-years of follow-up) in a cohort of patients with severely reduced left ventricular ejection fraction (<30%). Within another increased-risk population treated in the SHIELD trial 58% of the placebo-group experienced “all-cause shocks plus symptomatic tachyarrhythmias terminated by ATP”. The overall number of episodes was 1595 in 214 patients (average of ~7.5/patient and year).

## **Ertugliflozin to Reduce Arrhythmic burden in ICD/CRT patientS (ERASE-Trial) – a phase III Study**

### **2 Study Objectives and Endpoints**

#### **2.1 Primary and secondary objectives**

The primary objective of this study is to investigate the impact of Ertugliflozin on incident sustained ventricular tachycardia or ventricular fibrillation (sVT/VF) in patients with ICD±CRT therapy. Secondary objectives investigate the impact of Ertugliflozin on the number of therapeutic interventions of implanted devices, atrial fibrillation, and heart failure biomarkers.

#### **2.2 Primary, secondary and safety endpoints**

##### **2.2.1 Primary endpoint**

The primary endpoint is the number of incident sustained (>30 seconds) ventricular tachycardia or ventricular fibrillation (sVT/VF) from randomization to week 52.

##### **2.2.2 Secondary endpoints**

Secondary endpoints are as follows:

- The number of incident non-sustained ventricular tachycardia (nsVT) from randomization to week 52
- The number of appropriate ICD-treatment episodes from randomization to week 52
- The number of hospitalization due to heart failure from randomization to week 52
- The total number of hospitalization days from randomization to week 52
- The change in NTproBNP from randomization to week 52.
- The change in HbA1c levels from randomization to week 52.
- Cardiovascular mortality from randomization to week 52.

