2.4 Secondary outcomes

Secondary outcomes measures:

Difference in nsVT episodes between treatment groups from randomization to week 52

Difference in number of appropriate therapeutic ICD therapies between groups from randomization to week 52

Difference in the change of nt-proBNP levels between treatment groups from randomization to week 52

Difference in the change of HbA1c between treatment groups from randomization to week 52 (in subjects with known T2DM)

Difference in the number of hospital re-admissions due to heart failure between the treatment groups from randomization to week 56

Difference in the duration of hospital stay between the treatment groups after initiation of the study treatment from randomization to week 56

Difference in cardiovascular mortality between treatment groups from randomization to week 56

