5.6 Benefit-Risk Assessment

Ertugliflozin has been studied in subjects with type 2 diabetes as monotherapy as well as in combination with DDP-inhibitors as well as metformin. A cardiovascular safety study is ongoing(14). However, it has not been studied with respect to cardiac arrhythmias, yet. Other SGLT-2 inhibitors already finished the cardiovascular outcome trials(1; 15-17) demonstrating cardiovascular safety and beneficial effects, most prominent with respect to heart failure. A class effect can be assumed. Moreover, first data is published, demonstrating beneficial cardiovascular effects in non-diabetic patients with heart failure, too. As heart failure per se is a trigger for ventricular arrhythmias, every improvement in heart failure is likely to reduce ventricular arrhythmias, too.

With respect to diabetes it can be taken as given that the drug is not causing hypoglycaemic events per se, hypoglycaemia appears not to be a major issue in subjects without diabetes, that are studied in this trial as well. When ertugliflozin is used together with sulfonylurea or insulin, hypoglycaemia might occur and therefore participants will be instructed to reduce concomitant antihyperglycemic medication accordingly.

Fungal genital infections are the most common side effect of ertugliflozin and participants will be informed about this and instructed on prevention measures.

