### **3.3 Randomization**

After screening, all eligible patients for the trial will be randomised into one of the two arms of the study via Randomiser Software (Institute for Medical Informatics, Statistics and Documentation, Medical University of Graz, <http://www.randomizer.at>), which will be programmed with a randomisation schedule provided by an independent statistician. The randomisation will be stratified by site, by type 2 diabetes and by eGFR < 60 vs  $\geq$  60. Only the subject number will be recorded in the case report form (CRF). The investigator will maintain a personal subject identification list (subject numbers with the corresponding subject names) to enable records to be identified.

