## **Ertugliflozin to Reduce Arrhythmic burden in ICD/CRT patientS (ERASe-Trial) – a phase III Study**

**RR =  $e^{\beta_1}$ .** The efficacy of the drug, compared to placebo, will then be investigated by testing the following null and alternative hypotheses:

$$H_0: \beta_1 = 0 \quad \text{vs.} \quad H_A: \beta_1 \neq 0$$

The function `glm.nb` from the MASS package in R will be used for this reason and for fitting the negative binomial regression model. The model will also adjust for the baseline number of sVT/VF. Sensitivity analysis will be carried out by using methods robust to outliers.

The analysis of secondary endpoints will be as follows: The number of incident nsVT, the number of appropriate ICD-treatment episodes, the total number of hospitalization due to heart failure will be analysed using a beta binomial model. The change in NTproBNP and the change in HbA1c levels from randomization to week 52 will be analysed using a multiple linear regression model. Hospitalization days from randomization to week 52 will be compared between the two groups using mean and SD. Cardiovascular mortality will be analysed by comparing proportions across the two groups.

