### **5.1 Covariates and subgroups**

All analyses, including the primary analysis, will be adjusted for the variables used when stratifying the randomization if the sample size permits. Analysis may also be adjusted for baseline levels of the dependent variables if available. No subgroup analyses are planned.

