**Ertugliflozin to Reduce Arrhythmic burden in ICD/CRT patientS (ERASE-Trial) – a phase III Study**

## 7 Summary of Changes to the SAP

This is the revised version of the SAP. It was revised due to the early termination of the trial and the corresponding lower sample size.

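### SAP 2.2 and 5 do not match Protocol 2.2 and 2.4: the HbA1c analysis loses its restriction to known T2DM, the electric storm count is omitted, and three endpoints end at week 52 instead of week 56

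*SAP*

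**What the plan says.** **HbA1c.** Protocol 2.4 gives the outcome as "Difference in the change of HbA1c between treatment groups from randomization to week 52 (in subjects with known T2DM", and the synopsis carries the same limit. SAP 2.2.2 has only "The change in HbA1c levels from randomization to week 52". SAP 5 continues in the same way: "The change in NTproBNP and the change in HbA1c levels from randomization to week 52 will be analysed using a multiple linear regression model".

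SAP 5.1 states: "All analyses, including the primary analysis, will be adjusted for the variables used when stratifying the randomization if the sample size permits". T2DM is one of those variables, because SAP 3.3 describes randomisation as "stratified by site, by type 2 diabetes" and by eGFR. SAP 5.1 also states: "No subgroup analyses are planned".

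Patients without diabetes are in the trial. Protocol 5.6 remarks that "hypoglycaemia appears not to be a major issue in subjects without diabetes, that are studied in this trial as well". Table 2 in Protocol 5.5.5 has HbA1c drawn at both visits, with no condition on diabetes status.

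**Electric storm.** Protocol 2.2 lists eight safety items, one of them a count of ventricular electric storms. SAP 2.2.3 lists the other seven.

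**Window.** Protocol 2.4 follows HF re-admissions, hospital stay and CV mortality to week 56. SAP 2.2.2 ends all three at week 52. SAP 5 repeats week 52 for hospital days and gives no window for the other two. SAP 3.4 keeps Visit 3, four weeks after Visit 2, with adverse event collection.

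**Reason for revision.** SAP 7 says of the SAP: "It was revised due to the early termination of the trial and the corresponding lower sample size". It names no endpoint.

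**The concern.** The HbA1c difference matters most because it changes whose effect is estimated. The protocol asks about glycaemic effect in patients with known T2DM. The SAP's model pools them with patients whom the protocol left out of this outcome. A reader of the report who takes the figure as the T2DM effect would probably see it understated.

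The other two differences concern traceability. One arrhythmic safety item would have no planned tally, in a trial about arrhythmic burden. Three clinical endpoints would be counted over a window that the protocol does not use. With neither a match nor a recorded reason, nobody comparing report with protocol could tell a decision from an oversight.

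**Working it through.** The plan states no figure on this point, so there is none to reproduce. The check compares the two documents and then sizes the differences.

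**Comparison**

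| Item | Protocol 2.2 / 2.4 | SAP 2.2 / 5 |
|---|---|---|
| HbA1c change | known T2DM, week 52 | no T2DM limit, week 52 |
| HF admissions | week 56 | week 52 |
| Hospital stay / days | week 56 | week 52 |
| CV mortality | week 56 | week 52 |
| nsVT, ICD therapies, NT-proBNP | week 52 | week 52 |
| Electric storm count | listed | absent |

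Four of seven secondary endpoints differ in population or window, and one of eight safety items is missing.

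**HbA1c: numbers of patients.** Protocol 4 aims for more than 30% with T2DM. At 30% of the planned 402, 0.30 × 402 ≈ 121 have T2DM and 402 − 121 = 281 do not. The number enrolled at early termination is not given.

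**HbA1c: what the SAP model estimates.** Let p be the T2DM share, and f the effect without T2DM as a fraction of the effect with T2DM. With equal allocation, which the sample size section implies, a linear model with treatment and T2DM as main effects weights the two groups by their size:

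all-patient effect ÷ T2DM effect = p + (1 − p) × f

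The documents do not give f. The range 0 to 0.5 is an assumption, as is an upper value of 50% for p.

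| p | f = 0 | f = 0.5 |
|---|---|---|
| 0.30 | 0.30 | 0.30 + 0.70 × 0.5 = 0.65 |
| 0.50 | 0.50 | 0.50 + 0.50 × 0.5 = 0.75 |

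The ratio is therefore 30–75%. It reaches 100% only at f = 1. T2DM as a covariate removes between-group differences in mean change but leaves this weighted average as the target. Only a restriction, or a treatment-by-T2DM interaction, yields the T2DM effect, and SAP 5 and 5.1 specify neither.

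**HbA1c: cost in precision.** If residual SD is the same in both groups (assumption), restriction multiplies the standard error by 1/√p: 1/√0.30 = 1.83, or 1/√0.50 = 1.41.

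**Window.** Ending at week 52 removes 4 of 56 weeks, 4/56 = 7.1% of calendar time. The share of events is unknown. Visit 2 falls at week 52 ± 4, which is 48 to 56. Visit 3 follows 3 to 5 weeks later, so it falls between 48 + 3 = 51 and 56 + 5 = 61. If both windows were used evenly (assumption), the Visit 3 date is symmetric about week 52 + 4 = 56, so about 50% of contacts come before week 56. By the same reasoning about 3% come before week 52: the corner triangle has area 0.5 out of 8 × 2 = 16.

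**The case against.** The strongest reply is that these are harmonisation gaps and not analysis decisions. The SAP lags the protocol elsewhere: SAP 3.2.1 lacks the sVT/VF route in Protocol 4.1, and SAP 3.4 keeps a 6-minute walk test that Protocol 5.3 does not have. That the endpoint text was simply not updated is an inference, but a reasonable one. A reader might infer that the endpoints were altered without explanation when the trial stopped early. The documents do not support that. SAP 7 describes revision of the SAP and is not a log of departures from the protocol, and the preceding SAP is not available. All that can be said is that SAP 7 links its reason to none of these differences.

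A reader might also infer that late events vanish and that storms go unreported. Neither follows. Protocol 6.6 makes deaths and unexpected hospitalisations SAEs, Protocol 6.6.1 has them reported through follow-up, and SAP 2.2.3 puts no week-52 limit on SAEs or all-cause mortality. Events in weeks 52–56 are missing only from the three named endpoints. A storm that meets SAE criteria is captured as an SAE. What is lost is the separate tally, for which neither document gives a definition.

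On the window, week 52 is defensible. The drug supply covers 52 weeks (Protocol 9.1), the hypothesis in Protocol 1.2 refers to 12 months, and the last contact is a telephone call. This objection stands as far as the choice of week goes, but not for leaving the two documents in conflict.

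For HbA1c, the size of the dilution does depend on an assumed effect in patients without T2DM. The mismatch in population does not.

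**Conclusion.** The point holds, with HbA1c as its main part. As written, the SAP estimates an all-patient effect where the protocol specifies the effect in known T2DM, and nothing else in the SAP recovers the latter. On the assumed ranges the two differ by a factor of 0.30 to 0.75. With similar effects in both groups the difference would be small.

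The omitted storm count is a smaller and certain mismatch. The window is a conflict to be reconciled, covering 7.1% of calendar time with an unknown share of events.

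A reader might conclude that the protocol's week 56 should be restored and the SAP 5 comparisons left as they are. The documents do not support that. About half of the Visit 3 contacts could precede week 56, while SAP 5 compares hospital days by mean and SD and CV mortality by proportions, neither of which allows for unequal follow-up.

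The primary test is unaffected. SAP 5.4 leaves the secondary endpoints without type I error control, so the harm is to interpretation and to consistency with the protocol.

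**What to change.** - **HbA1c (SAP 2.2.2 and 5).** Restrict the analysis to patients with known T2DM. An all-patient analysis may be added and labelled supplementary. Cost: a less precise estimate, by the factors shown above.
- **Electric storm (SAP 2.2.3).** Restore the item. State one definition and tally it, blind to arm, from the arrhythmic events that Protocol 5.5.2 says are recorded. Cost: one extra count on existing data.
- **Window (SAP 2.2.2 and 5, Protocol 2.4).** Make the two documents agree.
  - If week 56 is kept, use a time-at-risk offset for HF hospitalisations and hospital days, and a time-to-event analysis with censoring at last contact for CV mortality. Cost: SAP 5 must change its methods, and some patients will lack data to week 56.
  - If week 52 is kept, record the change with date and reason. Cost: wording only.
- **SAP 7.** If the HbA1c or storm difference is deliberate, record it there too, with date and reason.
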